6.0 Data and Specimen Banking

- 6.1** All information will be stored in REDCap via a Children's Mercy secured iPad or laptop onto a secure Children's Mercy server by granted study staff.

7.0 Sharing of Results with Subjects

SHORT TITLE: SexHealth Mobile

7.1 All information collected will be deidentified before sharing results. We will have a short write up of the data for each recovery site to distribute to their clients.

8.0 Study Timeline

8.1 The duration of this study is estimated to be at 18 months to reach our target sample size. We estimate we will need approximately 6 months to recruit and enroll participants in the usual care period, and approximately 6 months during the intervention “SexHealth Mobile” period. There are 3 months included before recruitment for preparation (securing ethical approval, creating intervention and research tools, developing a manual of operations) and 2 months at the end for analysis.

8.2 The duration of the study for each participant will be 3 months.

	Month																	
	1	2	3	4	5	6	7	8	9	10	11	12	13	14	15	16	17	18
Preparation																		
Usual Care				Recruit				Follow-up										
Intervention									Recruit				Follow-up					
Analysis																		

9.0 Inclusion and Exclusion Criteria

9.1 Swope staff/clinician as a participant:

- is a current employee of Swope health services
- Practice or tasks are relevant to intervention

9.2 Inclusion Criteria for client participants

Participants will be eligible if they:

- are between the ages of 18-40 years
- are biological females
- have an unmet need for contraception (sexually active, able to become pregnant, not consistently/currently using these contraception methods [sterilization, subdermal implant, intrauterine device, injectable, pill, patch, or ring]
- have current or recent (within the past year) problematic patterns of substance use (according to the CAGE-AID self-assessment

9.3 Exclusion Criteria for subjects

Participants will be ineligible if they:

- have previously enrolled in the study
- are unable to provide informed consent
- are pregnant at index (recruitment) visit

10.0 Vulnerable Populations

10.1 Women with active addiction or in recovery may be vulnerable to undue influence because of unique challenges involving housing, relationships, and health. We will use these strategies to avoid situational vulnerability among potential participants: 1) provide written and verbal information about the study that is easy to understand (e.g., layman's terminology, no higher than 8th grade reading level); 2) provide clarifications and answer all questions about participation; 3) allow as much time as needed for prospective participants to make their decision about participation. We will build support from trusted community members who can facilitate research understanding (including voluntary nature). We will assist with referrals for women interested in learning more about contraception but who do not want to participate in our study.

11.0 Local Number of Subjects

11.1 We anticipate enrolling up to 170 new participants to reach out target sample size of 160 with evaluable data (up to 85 during the usual care period, and up to 85 during the intervention period). This is in addition to the 31 recruited in the first attempt to be in the study before COVID-19, meaning a total of 201 women will be enrolled in the study. Additionally, we will recruit up to 10 Staff/Clinicians from Swope Health Services.

12.0 Screening and Recruitment Methods

12.1 For the usual period, recruitment will occur through recovery sites at certain weekly rotations throughout the 6-month period. Participants will be presented with a recruitment flyer (virtually or in person) and ask if they are interested in participating by study staff. We will have a peer outreach coordinator at each site to help elicit participation interest. If a participant is interested, study staff will screen the participant for eligibility on REDCap via a tablet, their personal mobile device, or a computer available at their site.

12.2 During the intervention period, study staff will recruit at the recovery sites based on the mobile clinic's stop schedule. If MMU is not available, study staff will recruit based on certain weekly rotations that are provided by Swope's health care provider. Participants will be presented with a recruitment flyer (virtually or in person) and ask if they are interested in participating by study staff. We will have a peer outreach coordinator at each site to help elicit participation interest. If a participant is interested, study staff will screen the participant for eligibility via a tablet on REDCap.

12.3 All identifying information will be collected after participant has been screened and consented

13.0 Reimbursement, Payment and Tangible Property provided to subjects

13.1 Participants will be compensated up to \$70 for their time. Participants will receive \$20 at the recruitment visit. They will

receive \$15 for completing the two-week follow-up survey, another \$15 for completing the one-month follow-up survey, and \$20 for completing the three-month follow-up survey. There are no plans for the collection of SSN from participants.

14.0 Withdrawal of Subjects

14.1 Participants may withdrawal themselves from the study at any time. When a participant withdraws from a study, data collected on the participant to the point of withdrawal remains part of the study database and may not be removed. Discussion of enrolled participants will be held weekly to ensure they meet our inclusion and exclusion criteria.

15.0 Risks to Subjects

As with any study, there is potential for loss of confidentiality. Information security is top priority for both the investigators and the hospital. We believe that all identifying and clinical information will be secure, and a security breach is highly unlikely to occur. We acknowledge, however, should a security breach occur, it would have several serious consequences for the participant, including identity theft and loss of privacy.

There is potential for emotional distress while discussing sensitive material related to sexual health. Participants may skip a question or stop the study at any time. Due to the sensitive nature of some of our survey questions, we will offer printed resource material to all participants.

Risk of emotional distress: Women will receive detailed information about this study to minimize the risk of physical and emotional harm to study participants. Participants may experience increased stress over survey questions asking about sexual risk behaviors. However, we feel this risk is minimal and will include information in the consent process that reminds participants that they are not required to answer questions that make them feel uncomfortable. At each recovery site and at Swope Health, there are advocates available for patients and families, if needed. Clinical counseling sessions will be recorded and continuously reviewed for research quality purposes. In this study setting, if a participant expresses a concern or need that is outside of the scope of this project, we will refer those participants back to their SUD treating team, as is our standard practice. During the consent process, we will inform participants that most of the information they share during the study will be kept confidential except in rare cases where their safety is at risk or mandated reporting is in effect.

Risk of device removal: Participants who choose to start a subdermal contraceptive implant during the study and need removal of the implant within one year of placement, the cost of the implant removal will be paid for by the study. If participant has an expired implant or IUD that needs to come out and chooses to have the device removed at enrollment, the cost for removal of the expired implant will be paid for by the study. Swope staff members will be responsible for removing devices at enrollment on the medical mobile unit.

16.0 Potential Benefits to Subjects

16.1 There may be no direct benefit to participating in the study as the SexHealth intervention is not a research intervention. Participants may benefit from the additional monitoring that will occur as part of the follow-up survey visits.

17.0 Investigator Assessment of Risk/Benefits Ratio: (IRB makes the final determination) *Based upon your response in Sections 17.0 and 18.0, please provide your assessment of risk and benefits in below table.*

Select as applicable:	Pediatric Risk Category:	
	Category 1	Research not involving greater than minimal risk (45 CFR §46.404 and 21 CFR §50.51)
	Category 2	Research involving greater than minimal risk but presenting the prospect of direct benefit to the individual subjects. (45 CFR §46.405 and 21 CFR §50.52)
	Category 3	Research involving greater than minimal risk and no prospect of direct benefit to individual subjects, but likely to yield generalizable knowledge about the subject's disorder or condition. (45 CFR §46.406 and 21 CFR §50.53)
	Category 4	Research not otherwise approvable which presents an opportunity to understand, prevent, or alleviate a serious problem affecting the health or welfare of children. (45 CFR §46.407 and 21 CFR §50.54)
Select if applicable:	Adult Risk Category:	
X	Not Greater than Minimal Risk	
	Greater than Minimal Risk	

18.0 Data Management and Confidentiality

18.1 Statistical Methods:

Demographic variables collect from both control and intervention participants will be summarized and compared. Categorical variables will be reported as frequencies and percentages; whereas, continuous variables will be reported as means with standard deviations or medians with interquartile ranges depending on which is more appropriate. Fidelity will be assessed through analyzing recordings using a checklist developed for the delivery of the training. Differences between groups regarding the usage of highly effective contraception at 1-month post enrollment will be compared using a Fisher's Exact Test. We will also compare contraception usage at 2-weeks and 3-months post enrollment. Baseline and follow-up survey data will also be summarized and compared. Likert-scale items will be compared using Wilcoxon Mann Whitney tests. To assess the primary outcome, logistic regression models will be fit to investigate potential predictors for utilizing highly effective contraception at the post enrollment time points.

All statistical tests will be conducted at the alpha = 0.05 level. Statistical analysis will be done using The SAS software v 9.4 (Copyright, SAS Institute Inc. SAS and all other SAS Institute Inc. product or service names are registered trademarks or trademarks of SAS Institute Inc., Cary, NC, USA) and R statistical software (R Core Team (2015). R: A language and environment for statistical computing. R Foundation for Statistical Computing, Vienna, Austria. URL <http://www.R-project.org/>).

18.2 Multiplicity:

We are powered to test our primary hypothesis for both the entire sample as well as the subsample of women with OUD in both the usual care and interventional groups. Survey responses collected at baseline and follow-up will have multiple items which will be compared and adjusted for multiple comparisons using a Bonferroni correction.

18.3 Power/Sample Size:

This n is based on Fisher's exact test assuming uptake of 20% in the baseline period and 76% in the intervention period (based on studies showing uptake of point-of-care contraception among active drug users [66%] and women in recovery [85%]). Assuming 90% power and an error probability of $\alpha = 0.05$, this calculation gives us starting sample size of 32. Because we want to show statistically significant effects for both women with any type of SUD including those with OUD, and estimating that 30% of the study population will have OUD (according to estimates from our partner sites), we want to finish with 107 women with in total (30% of this is 32). To protect against attrition with this highly transient population, we will oversample our total by 50%, bringing our total N=160 (107x1.5).

18.4 Data Management:

To minimize risk of possible breach of confidentiality, data will be entered and stored into REDCap by study staff. Data will be stored on a CM secure network via CM encrypted password protected tablet and laptop. Participants will be assigned a unique REDCap ID number for management of their data collection. Online consent forms will minimize risk of transporting PHI back to CM from the recruitment sites.

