– **Our primary hypothesis** is that current use of highly effective contraception (includes *sterilization, subdermal implant, intrauterine device, injectable, pill, patch, or ring*) will be greater at 1-month post-enrollment among women recruited during the intervention period (i.e., “SexHealth Mobile”) compared to those recruited during the usual care period. We will also compare current use and discontinuation rates at 2-weeks and 3-months among all participants.

1.2 Our secondary objective is to explore intervention feasibility.

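### Fisher's exact test is valid but conservative for the OUD subsample that sets the trial's size; Boschloo's exact test would recover about 1 to 5 points of power at or near an even split, depending on sidedness and the split

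*Combined protocol and SAP*

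**What the plan says.** Section 18.1 names the test for the primary outcome: "Differences between groups regarding the usage of highly effective contraception at 1-month post enrollment will be compared using a Fisher's Exact Test". It adds that "All statistical tests will be conducted at the alpha = 0.05 level", without saying one-sided or two-sided. The primary hypothesis in section 1.1 is directional: use "will be greater at 1-month post-enrollment among women recruited during the intervention period".

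Section 18.3 uses the same test for the sample size, "assuming uptake of 20% in the baseline period and 76% in the intervention period", with 90% power and alpha 0.05, and reports that "this calculation gives us starting sample size of 32". It then makes that 32 the OUD requirement: "we want to finish with 107 women with in total (30% of this is 32"). Adding 50% for attrition gives 160 enrolled.

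Section 18.2 claims power for two populations: "We are powered to test our primary hypothesis for both the entire sample as well as the subsample of women with OUD". The study summary fixes 80 evaluable women per period overall. Nothing fixes the number of OUD women per period; the 30% share is an estimate from the partner sites.

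**The concern.** Fisher's test conditions on the total number of contraception users as well as on the group sizes. With about 16 women per group, few tables share any given total, so the attainable p-values are far apart and the true type I error falls well below the nominal 5%. The number of users is not fixed by this design. An unconditional exact test, such as Boschloo's, therefore applies. It takes Fisher's p-value as its statistic and sets the cut-off so that the maximum type I error over all common rates is at most 5%. Its rejection region contains Fisher's, so it cannot have less power.

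At stake is the OUD comparison. It is the smaller of the two comparisons that 18.2 says are powered, and it determines the total N. More power from the same women matters in a population where 18.3 already allows for heavy attrition.

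**Working it through.** **Inputs from the documents.** Uptake 20% v 76%; alpha 0.05; power 90%; 32 women in total (18.3); OUD completers 0.30 × 107 ≈ 32 (18.3); no-attrition case 0.30 × 160 = 48; lower cited uptake 66% (18.3).

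**Assumptions.** The documents do not state sidedness, so both were run. They do not state the OUD split; 16 v 16 is the even case and others were run.

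**Method.** For n₁ usual-care and n₂ intervention women, enumerate every table (a, b) of users.
- Power = Σ Bin(a; n₁, 0.20) × Bin(b; n₂, 0.76) over tables that the test rejects.
- Size = maximum over a common rate π from 0.001 to 0.999 of Σ Bin(a; n₁, π) × Bin(b; n₂, π) over the same tables.
- Fisher rejects when its p ≤ 0.05. Boschloo rejects when Fisher's p ≤ c, where c is the largest attainable value that keeps the size at or below 0.05.

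**Step 1: the plan's own figure.** One-sided Fisher at 0.05 has power 89.7% at 15 per arm and 92.6% at 16 per arm. The smallest equal-group N reaching 90% is therefore 32, as the plan says. Two-sided Fisher gives 85.4% at 16, 89.2% at 17 and 92.1% at 18 per arm, so N = 36. Of these two Fisher calculations, only the one-sided one returns 32.

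**Step 2: one table where the tests differ.** Take 3 of 16 users in usual care and 9 of 16 in the intervention period (12 users in all). The lower tail is

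[C(16,3)C(16,9) + C(16,2)C(16,10) + C(16,1)C(16,11) + C(16,0)C(16,12)] / C(32,12)
= (6,406,400 + 960,960 + 69,888 + 1,820) / 225,792,840 = 0.0329.

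With equal groups the two-sided p is twice this, 0.0659. Fisher does not reject. Boschloo's cut-off at 16 v 16 is c = 0.073, so it does, with the maximum type I error still below 5%.

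**Step 3: two-sided 0.05, 20% v 76%.**

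| Usual care / intervention | Fisher size | Fisher power | Boschloo power | Gain (points) |
|---|---|---|---|---|
| 16 / 16 | 2.0% | 85.4% | 90.5% | 5.1 |
| 15 / 17 | 3.4% | 89.2% | 90.6% | 1.4 |
| 17 / 15 | 3.4% | 88.2% | 90.8% | 2.5 |
| 14 / 18 | 2.8% | 87.3% | 88.4% | 1.2 |
| 18 / 14 | 2.8% | 87.3% | 89.2% | 2.0 |
| 12 / 20 | 3.2% | 84.7% | 90.9% | 6.2 |
| 20 / 12 | 3.2% | 85.4% | 91.2% | 5.7 |

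Gains are taken before rounding. Boschloo's size at 16 v 16 is 4.1%. Averaged over splits of 32 with binomial(32, 0.5) weights, Fisher has size about 3.0% and power 86.8%, against 90.0% for Boschloo, a gain of about 3.1 points.

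**Step 4: other settings.**
- One-sided 0.05, 16 v 16: Fisher size 2.5%, power 92.6%; Boschloo size 4.3%, power 94.5%. Gain 1.9 points.
- No attrition, 24 v 24, two-sided: 97.7% to 98.4%. Gain 0.7 points.
- Intervention uptake 66%, 16 v 16, two-sided: 65.0% to 75.3%. Gain 10.3 points.
- Whole sample at 20% v 76%, 53 v 54 (107 split evenly) or 80 v 80: about 100% with either test. At 66% and 53 v 54: 99.85% against 99.90%.

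**The case against.** Fisher's test controls the type I error, and it is the test on which N was based, so analysis and sizing agree. Conservatism from discreteness is a known property of a valid test, not a defect. This stands, and the point is one of efficiency only.

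The 2.0% size and the 5.1-point gain belong to a two-sided test at exactly 16 v 16. One woman moved between groups raises Fisher's size to 3.4% and cuts the gain to 1.4 or 2.5 points. This also stands. The gain does not fall steadily with imbalance, since 12/20 and 20/12 return about 6 points, so a range is the honest summary.

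The shortfall from 90% arises only if the test is two-sided. On the one-sided reading, which fits the directional hypothesis and reproduces 32, Fisher already has 92.6% at 16 v 16. Changing the test should therefore not be used to cover an unstated choice of sidedness; that must be settled first.

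A reader might infer that the primary comparison as a whole loses about 5 points. The documents do not support that: the primary hypothesis covers all women recruited, and at the planned rates that comparison loses nothing. A reader might also infer that Boschloo's test guarantees 90% in the OUD women. It does not: at 14/18 it gives 88.4% and at 18/14 it gives 89.2%, and the split is not controlled.

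**Conclusion.** The point holds as a cheap improvement for the OUD comparison. With 32 OUD women, Fisher's true size is about 2% to 3.4% at the near-even splits (14/18 to 18/14), whichever side is tested at 16 v 16. Boschloo's test keeps type I error at or below 5% and had more power in every 32-woman setting computed. At 20% v 76% the gain is 5.1 points two-sided at 16 v 16, 1.2 to 2.5 points at the neighbouring splits and 1.9 points one-sided at 16 v 16. It shrinks to 0.7 points if nobody is lost, and it is much larger if uptake is nearer 66%. These figures rest on the plan's uptake rates, its 30% OUD share, and an assumed sidedness and split.

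It does not follow that the plan's test is wrong or that its 32 is miscalculated, since a one-sided Fisher calculation gives exactly that number. If the test is meant to be two-sided, however, 18.3's 90% at 32 is not met by Fisher's test at 16 v 16 (85.4%).

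**What to change.** Before outcome data are examined:
1. State in 18.1 whether the 1-month test is one-sided or two-sided.
2. Name Boschloo's unconditional exact test at 0.05 for the 1-month OUD comparison, and for the whole sample for consistency. Keep Fisher's p-value as a supporting figure.
3. Re-quote the power in 18.3 for the chosen test and sidedness, giving a range over plausible OUD splits and noting that the split is not controlled.

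The cost is a sentence or two in 18.1, a revised paragraph in 18.3, and a short piece of code in R, which 18.1 already lists. No extra participants are needed. The downside is a less familiar test whose p-value needs numerical maximisation over the common rate, so the software and version should be recorded.

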1.0 Study Summary

Study Title	A quasi-experimental, interrupted time series study to evaluate the effectiveness of “SexHealth Mobile” on uptake of contraception in women with substance use disorder
Study Design	A quasi-experimental study design using an interrupted time series (i.e., usual care [control] then intervention care) to compare uptake of contraception before and after implementing the “SexHealth Mobile” intervention.
Primary Objective	To improve access to highly effective contraception among women with substance use disorder (SUD) with our pilot program “SexHealth Mobile”.
Secondary Objective(s)	To explore intervention feasibility
Research Intervention(s)/ Investigational Agent(s)	Our study intervention consists of “SexHealth Mobile” which integrates two existing services in our community: a mobile medical unit (MMU) operated by Swope Health Services, and “SexHealth” a point-of-care contraception counseling service that our research team developed for Children’s Mercy Hospital’s emergency department (ED).
IND/IDE #	N/A
Study Population	Study population includes women with substance abuse disorder (SUD) with an unmet need for contraception who are accessing health, recovery, or community services recovery sites committed to our community partner, Swope Health Services. We will also enroll staff and clinicians from Swope Health who will perform tasks (including contraceptive counseling) relevant to health care delivery in the mobile medical unit.
Sample Size	Total sample size is: Women with SUD = 160 (We need 160 with evaluable data at end of index visit with 80 in each time period so will request to enroll up to 170 if needed) – Usual Care [control]: up to 85 – SexHealth Mobile intervention: up to 85 Staff/Clinicians from Swope Health Services = 10
Study Duration for Individual Participants	Women with SUD = Total study duration will be 3 months for all participants. Follow-ups will be conducted at 2-weeks, 1-month, and 3-month post-enrollment. Staff/Clinicians from Swope Health Services = 18 months
Study Specific Abbreviations/ Definitions	SUD: substance abuse disorder OUD: opioid use disorder MMU: Swope’s medical mobile unit ED: emergency department

Objectives and Hypotheses

1.1 Our primary objective is to improve access to highly effective contraception among women with substance use disorder (SUD) with our pilot program “SexHealth Mobile”.

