5.0 Procedures Involved

5.1 Study Design:

A quasi-experimental study with an interrupted time series (i.e., usual care [control] then intervention care) to compare the uptake of contraception before and after implementing the "SexHealth Mobile" intervention. Participants recruited will be women with SUD/OUD with an unmet need for contraception who are accessing health, recovery, or community services at centers where Swope Health already provides clinical care (but not contraception). The recovery centers include: Healing House, ReDiscover, Journey to a New Life, and Amethyst Place. We are partnering with Swope Health Services to integrate the "SexHealth Mobile" model into their existing MMU that currently provides limited clinical services.

5.2 Research Procedures:

Usual care: Study staff will work with a point person at each of the recovery sites to facilitate recruitment logistics according to the site's COVID- related restrictions. Recruitment will continue until the target sample size has been reached (up to 6 months). Staff will work with recovery sites to reach and identify women that may be interested and meet eligibility criteria.

Study staff will distribute recruitment information virtually to the sites in the form of electronic recruitment document. We will also create a video with recruitment information for the sites to distribute.

SHORT TITLE: SexHealth Mobile

Interested participants may be given options to meet in-person or call-in information for a TEAMS meetings that will serve as recruitment sessions. Women will speak to a member of the study staff, complete eligibility, informed consent, and the baseline survey. In-person recruitment may also occur. In this case, we will use our approved COVID-19 contingency plan to minimize risk of COVID transmission, including using outdoor spaces, wearing masks, maintaining social distance, and sanitizing all materials. We will also adhere to participating sites COVID-19 safety guidelines during this time.

During recruitment, women will complete an eligibility screen, informed consent, and baseline survey via REDCap surveys. All participants will be assigned a unique patient identifying number through REDCap.

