Our multi-disciplinary team developed the assessment tools, based on national surveys and a review of the pertinent literature including validated items where applicable. At baseline, we will assess for high-risk sexual behaviors, substance use, relationship status, health care access and utilization, health history (e.g., pregnancies, mental health), and demographic information. Follow-up surveys will assess for contraception use (including condoms), healthcare utilization, health history, intervention satisfaction and feasibility.

Baseline information will be collected directly from participants on an iPad recorded on REDCap. Follow-up surveys will be completed after enrollment and recorded in REDCap.

See our measure tools to know what demographic, baseline, and follow-up data will be collected.

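### Section 18.1 gives no method that uses a woman's own baseline answer for survey items asked at both baseline and follow-up

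*Combined protocol and SAP*

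**What the plan says.** The survey analysis is described in two places. Section 18.1 states: "Baseline and follow-up survey data will also be summarized and compared. Likert-scale items will be compared using Wilcoxon Mann Whitney tests". Section 18.2 adds: "Survey responses collected at baseline and follow-up will have multiple items which will be compared", with a Bonferroni correction. Neither section says whether the contrast is between periods or within woman, or at which time point it is made. The only model with covariates in 18.1 is a logistic regression for use of highly effective contraception. It does not cover the survey items.

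Section 5.4 gives the survey content. The baseline survey includes "relationship status, health care access and utilization, health history", along with sexual behaviours, substance use and demographics. For follow-up it says: "Follow-up surveys will assess for contraception use (including condoms), healthcare utilization, health history, intervention satisfaction and feasibility". So healthcare utilization and health history are named at both times, while satisfaction and feasibility are named only at follow-up. Item wording and response scales are left to measure tools that are not part of the document.

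Section 5.1 describes the design as "A quasi-experimental study with an interrupted time series (i.e., usual care [control] then intervention care"). The study summary sets the numbers: "We need 160 with evaluable data at end of index visit with 80 in each time period".

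**The concern.** A Wilcoxon-Mann-Whitney test compares two independent samples and has no place for a baseline value. For an item asked twice, that matters under either way of reading 18.1.

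- **Period against period at follow-up.** Whatever difference the cohorts had at enrolment persists in proportion to the correlation between a woman's two answers, and the test counts it as a difference between periods. The baseline answer would also have explained part of the follow-up variation, so precision is lost.
- **Baseline against follow-up in the same women.** The two samples are the same people, so the independence the test assumes is false.

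A baseline difference is plausible here. Allocation is by calendar period. Recruitment follows site rotations in usual care (12.1) but the mobile clinic's stop schedule in the intervention period (12.2). Section 5.2 also has staff build interest in the clinical service around the start of that second period. Health care use, a domain asked at both times, could well differ between women recruited in these two ways.

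**Working it through.** **The plan's own figures.** The plan states no power or sample size for survey items, so there is no figure to reproduce on this point. The completer target in 18.3 supplies the group size. 32 / 0.30 = 106.7, rounded to 107, and 107 × 1.5 = 160.5, given as 160. 107 / 2 gives about 53 women per period at follow-up. With no attrition it would be 80.

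**Assumed inputs, not in the documents.** A 5-level item; correlation r between baseline and follow-up answers of 0.3, 0.5 or 0.7; baseline difference b between cohorts of 0.3 or 0.5 SD; true effect 0.4 SD for power; level 0.05 for a single item.

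**Mechanism.** With no intervention effect, the expected follow-up difference is r × b. Take r = 0.5, b = 0.3 and 53 per period:
- difference = 0.5 × 0.3 = 0.15 SD
- standard error = √(2/53) = 0.194 SD
- standardised difference = 0.15 / 0.194 = 0.77
- rejection rate ≈ Φ(−1.96 + 0.77) + Φ(−1.96 − 0.77) = 0.117 + 0.003 = 0.12

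So a nominal 5% test rejects about 12% of the time. Adjusting for baseline removes the r × b term and multiplies the residual variance by 1 − r², which is 0.91, 0.75 or 0.51.

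**Simulation, 53 per period, 2,000 runs per setting.** Wilcoxon-Mann-Whitney (WMW) on follow-up is set against regression on period plus the baseline answer. Monte Carlo standard error is √(0.05 × 0.95 / 2000) = 0.5 points near 5%, and √(0.5 × 0.5 / 2000) = 1.1 points near 50%.

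| r | False positives, b = 0.3: WMW / adjusted | False positives, b = 0.5: WMW / adjusted | Power, effect 0.4 SD, b = 0: WMW / adjusted |
|---|---|---|---|
| 0.3 | 7.8% / 4.8% | 11.7% / 6.0% | 49.2% / 52.3% |
| 0.5 | 10.7% / 4.4% | 22.2% / 5.1% | 47.7% / 56.4% |
| 0.7 | 17.6% / 5.5% | 37.6% / 5.4% | 49.3% / 70.1% |

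With rank ANCOVA as the adjusted method, a repeat run gives WMW false positives of 7%, 12% and 17% (b = 0.3) and 11%, 24% and 39% (b = 0.5), against 5% to 6% adjusted. Power is 48% against 50%, 57% and 71%. The two runs agree within simulation error.

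**More women do not help.** At 80 per period the WMW false-positive rates are 8%, 15% and 26% (b = 0.3) and 13%, 32% and 55% (b = 0.5). The adjusted rates stay at about 5% to 6%. Power is about 66% against 69%, 75% and 86%.

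**Within-woman reading, 53 women.** WMW applied to paired answers has true size of about 2%, 1% and 0% at r = 0.3, 0.5 and 0.7. Its power for a 0.4 SD change is 48%, against 58%, 72% and 88% for the signed-rank test. Here the error is lost power, not excess false positives.

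**Effect of Bonferroni.** The number of items is not given. If there were 10, each would be tested at 0.05 / 10 = 0.005. At 53 per period and r = 0.5 to 0.7, WMW false positives fall to roughly 2% to 4% (b = 0.3) and 6% to 12% (b = 0.5). These are small in absolute terms but still several times the 0.5% intended per item.

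**The case against.** The strongest reply is that no affected item is shown to exist. The Wilcoxon-Mann-Whitney sentence covers Likert items only, and the domains most naturally put on a Likert scale, satisfaction and feasibility, appear only at follow-up. Healthcare utilization and health history may be counts or yes/no facts. This stands as a limit on scope: the number and scale of repeated items are unknown. It does not remove the point, because 18.1 names no baseline-adjusted or paired method for a survey item of any type.

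A reader might infer that the plan will report baseline differences as intervention effects. The documents do not support that. Section 18.1 gives no contrast or time point and does not say how survey differences will be interpreted. Baseline data are also to be compared, so an imbalance would be visible, though not adjusted for. For comparing baseline Likert items between cohorts, Wilcoxon-Mann-Whitney is a valid choice.

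It is also fair to say that the rates above rest entirely on assumed inputs, that the single-item figures at 0.05 are not those of the plan with Bonferroni, and that at r = 0.3 the gain in power is only about 3 points. Finally, the survey comparisons are secondary and no power is claimed for them. All of this stands and lowers the priority.

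**Conclusion.** The point holds for survey items asked at both baseline and follow-up, and only for those. For such items the plan names no analysis that uses the baseline answer. Under the assumptions above (53 per period, r 0.3 to 0.7, baseline shift 0.3 to 0.5 SD, single-item level 0.05), an unadjusted comparison of periods gives about 7% to 39% false positives against about 5% to 6% adjusted. For a 0.4 SD effect with equal baselines, power is about 48% to 50% against 50% to 71%. If the cohorts happen to be alike at baseline, only the loss of precision remains. Bonferroni scales the absolute rates down and leaves the bias in place.

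A reader might extend this to the 1-month contraceptive-use test. That would be wrong: section 9.2 requires an unmet need at entry, so women start as non-users or inconsistent users of the listed methods, and this point leaves that test untouched. Nor would adjustment for one baseline answer remove other confounding between periods. The adjusted rate of about 5% assumes that the baseline item is the only way in which the cohorts differ. This is a free improvement of low priority.

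**What to change.** In 18.1, state the contrast and follow-up time point for each survey item, and then:

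- **Items asked at both baseline and follow-up:** compare periods at the stated follow-up with a model that includes the woman's own baseline answer. Use proportional-odds regression for Likert items and logistic regression for yes/no items; rank ANCOVA is an alternative for ordinal items.
- **Any within-woman comparison of baseline with follow-up:** use a paired test, Wilcoxon signed-rank for ordinal items and McNemar for yes/no items.
- **Likert items asked once, such as satisfaction, and baseline Likert items compared between cohorts:** keep Wilcoxon-Mann-Whitney.

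Add a sentence acknowledging that this adjustment does not deal with other differences between the periods. The Bonferroni rule in 18.2 can stay as it is.

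The cost is a few sentences. The baseline answers are already collected, the methods are standard in the SAS and R software named in 18.1, and no further women are needed.
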